8.2. Participant Exclusion Criteria

Each eligible participant must not:

For All

1. Have been diagnosed with and/or treated for any type of cancer (excluding successfully treated locally excised basal cell carcinoma and melanoma in situ) within the past year prior to Screening.
2. Plans to undergo elective surgery during participation in the study.
3. Have current or recent suicidality, defined as follows:
 - Suicidal ideation within the past month, as evidenced by a "Yes" on question 4 (active suicidal ideation with some intent to act, without specific plan) or question 5 (active suicidal ideation with specific plan and intent) on the C-SSRS.
 - Suicidal behavior within the past year, as evidenced by a "Yes" on any of the C-SSRS Suicidal Behavior items (actual attempt, interrupted attempt, aborted attempt, preparatory acts or behavior, or suicidal behavior) on the C-SSRS.
 - Presenting a serious risk of suicide in the opinion of the investigator.
4. Take any psychotropic medications, including antidepressants and anxiolytics, unless the dose and frequency have been stable for at least 30 days prior to the first IP administration and are expected to remain stable for the duration of the study.
5. Have an ongoing medical or psychiatric condition that, in the opinion of the investigator, may compromise the participant's safety or compliance with study requirements.
6. Have supine vital signs outside of the following ranges at Screening or Baseline (vital sign measurements may be repeated once for initial values outside these ranges):
 - Heart rate <50 or >100 bpm,
 - Systolic blood pressure <100 or >160 mmHg,

- Diastolic blood pressure <60 or >100 mmHg.

7. Have an alcohol or drug use disorder within the past 2 years, as assessed by the investigator. A positive urine drug screen is exclusionary unless deemed by the investigator to reflect a prescribed medication.
8. Have a history of significant hand injury that would preclude either writing or rapid bimanual computerized responding.
9. Have a history of seizures or epilepsy, with the exception of a single episode of febrile seizures in childhood.
10. Have a history, presence, and/or current evidence of serologic positive results for human immunodeficiency virus (HIV)-1 or HIV-2 or hepatitis B or C.
11. Have a history of brain surgery, a significant head injury causing loss of consciousness greater than 30 minutes, or hospitalization due to a brain injury.
12. Have a history, presence, and/or current evidence of intracranial abnormality (eg, stroke, hemorrhage, space-occupying lesion).
13. Have a positive pregnancy test, is lactating, or intend to breastfeed during the study.
14. Be investigative site personnel, sponsor personnel, or an immediate member of their family (spouse, parent, child, or sibling whether biological or legally adopted).
15. Have participated in a previous clinical study of SAGE-718; have previous exposure to gene therapy; or have participated in any Huntington's Disease (HD) investigational drug, biologic, or device trial within 180 days, or a non-HD drug, biologic, or device trial within 30 days or 5 half-lives (whichever is longer).
(Note: Participants with confirmation of enrollment in the placebo arm of these trials would not be excluded.)
16. Receive any prohibited medications within 30 days of Screening and during participation in the study:
 - a. Other medications given at doses or in combinations that are likely to have a deleterious effect on cognitive performance, as determined by the investigator.
 - b. Tetrahydrocannabinol (THC)-containing substances (any route of administration), regardless of whether or not they are prescribed.
17. Is known to be allergic to any of SAGE-718 excipients, including soy lecithin.

Additional criteria for participants with HD only

18. Had gastric bypass surgery, has a gastric sleeve or lap band, or has had any related procedures that interfere with gastrointestinal transit.
19. Receive any prohibited medications within 30 days of Screening and during participation in the study:
 - a. Medications with potent effects at the NMDA receptor, including memantine, amantadine, ketamine, cycloserine, or related compounds.
 - b. Medications that inhibit cholesterol absorption (eg, ezetimibe).

- c. Bile acid sequestrants (eg, colestevolam, colestipol, cholestyramine).
- 20. Have a diagnosis of an ongoing neurodegenerative condition other than HD, including but not limited to Alzheimer's Disease, vascular dementia, dementia with Lewy bodies, or Parkinson's Disease.

Additional criteria for HP only

- 21. Have a diagnosis of an ongoing neurodegenerative condition, including but not limited to HD, Alzheimer's Disease, vascular dementia, dementia with Lewy bodies, or Parkinson's Disease.

8.3. Screen Failures

Screen failures are defined as participants who consent to participate in the clinical study but are not subsequently assigned to study intervention/entered in the study. A minimal set of screen failure information will be collected, including demography, screen failure details, eligibility criteria, and any AE or SAE.

Individuals who do not meet the criteria for participation in this study (screen failure) may be rescreened once, with the approval of the medical monitor. Rescreened participants will be assigned a new participant number.

8.4. Investigational Product Discontinuation and Early Termination from the Study

A participant may withdraw from the study at any time at his/her own request for any reason. The investigator may discontinue a participant from the study and/or from IP for safety, behavioral, compliance, or administrative reasons.

The reason for IP discontinuation and/or the reason for ET from the study must be documented in the participant's study record and recorded in the participant's electronic case report form (eCRF).

The investigator must notify the sponsor and/or the medical monitor when a participant stops participation in the study for any reason.

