During the Treatment Period, participants with HD will be able to receive IP as long as there are no dose-limiting safety/tolerability concerns. Participants with HD who discontinue IP early should complete the remaining study visits as scheduled, unless the participant with HD withdraws consent or loses the capacity to grant consent. If a participant with HD withdraws from the study or stops study participation, an early termination (ET) visit should be conducted.

After completing the Treatment Period or Reliability Assessment Period, all participants will return to the clinic for follow-up visits on Day 42 (± 2 days) to collect continued safety and efficacy data.

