8.4.1. Investigational Product Discontinuation

Participants who discontinue IP will be invited by the investigator to complete all of the scheduled study visits and assessments through the end of the Treatment Period. Those who decline to continue participation will be asked to complete an ET Visit.

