8.4.2. Early Termination from the Study

At the time of study withdrawal/stopping study participation, if possible, an ET visit should be conducted. The participant will be permanently discontinued both from the IP and from the study at that time.

If the participant withdraws consent for disclosure of future information, the sponsor will retain and continue to use any data collected before such a withdrawal of consent.

If a participant withdraws from the study, he/she may request destruction of any samples taken and not tested, and the investigator must document this in the site study records.

Possible reasons for study discontinuation include but are not limited to the following:

- AE
- Pregnancy
- Protocol deviation
- Non-compliance with study drug
- Lost to follow-up
- Withdrawal by subject
- Screen failure
- Study terminated by sponsor
- Physician decision
- Other

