13.5. Efficacy Analysis

Efficacy data will be summarized using appropriate descriptive statistics and other data presentation methods, where applicable; participant listings will be provided for all efficacy data. Participants will be analyzed according to randomized treatment.

Baseline differences between participants with HD and HP will be assessed across candidate endpoint based on enrollment set using T-test. The mean differences, its 95% confidence interval (CI) and corresponding p value will be reported. For a given endpoint, if the 95% CI does not span zero, then it will be concluded that the participants with HD are statistically significantly different from their healthy comparators at Baseline for that endpoint; otherwise, it will be concluded that there is not enough evidence to declare them statistically different.

Additional analyses will be detailed in the SAP.

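### Sections 8.4 and 8.4.2 of the protocol allow study participation to be ended for non-compliance or a protocol deviation, which does not fit the Section 7.1 rule that participants with HD who stop IP stay in scheduled visits

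*Protocol*

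**What the plan says.** Three parts of the protocol bear on whether a participant with HD keeps attending visits.

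- **Retention after stopping IP.** Section 7.1 says that participants with HD who stop IP early "should complete the remaining study visits as scheduled, unless the participant with HD withdraws consent or loses the capacity to grant consent". Section 7.1.3 and SAP Section 5.1 repeat this. The next sentence of Section 7.1 reads: "If a participant with HD withdraws from the study or stops study participation, an early termination (ET) visit should be conducted". It gives no grounds for leaving.
- **Ending participation.** Section 8.4 states: "The investigator may discontinue a participant from the study and/or from IP for safety, behavioral, compliance, or administrative reasons". Section 8.4.2 says of a participant who leaves: "The participant will be permanently discontinued both from the IP and from the study at that time". Its list of reasons opens with "Possible reasons for study discontinuation include but are not limited to the following" and includes "Non-compliance with study drug" as well as protocol deviation, physician decision and other.
- **A third version.** Under Section 8.4.1, participants who discontinue IP are "invited by the investigator to complete all of the scheduled study visits and assessments through the end of the Treatment Period". This is an invitation, and it stops short of Day 42.

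On analysis, Protocol Section 13.5 says: "Participants will be analyzed according to randomized treatment". FAS1 and FAS2 (SAP Section 7.1) require a baseline and at least one post-baseline efficacy evaluation. Protocol Section 13.2 uses non-missing data, with imputation only if needed.

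**The concern.** A participant taken out of the study for missed capsules stops both IP and visits, for a reason outside the two exceptions in Section 7.1. Sites can read the two rules differently. Section 10.5.1.1 refers consistent non-compliance to the medical monitor for discussion but sets no criterion for removal.

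Protocol deviation has the same problem. Section 9.2.2 permits a prohibited medication when the participant's welfare needs it and records it as a deviation. Section 8.4.2 lists a deviation as a possible reason to leave the study.

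Missed doses do not make later measurements uninformative in a comparison by randomised arm. The HD cohort is selected for a MoCA score of 15 to 25, so adherence may plausibly be related to cognition, and it may also reflect tolerability. Exits on this ground could then depend on the outcomes being measured and move the drug-placebo comparison toward adherent participants. They would also end scheduled safety observation in people who may have stopped capsules because of symptoms.

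**Working it through.** **1. The passages side by side.** Take a participant with HD who repeatedly misses doses, has not withdrawn consent and retains capacity.

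- Under 7.1, 7.1.3 and SAP 5.1: if IP is stopped, the remaining visits should go ahead.
- Under 8.4 and 8.4.2: the investigator may end study participation for compliance, after which both IP and visits stop.
- Under 8.4.1: if IP alone is stopped, the participant is invited to continue to the end of the Treatment Period.

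The same person can have three different follow-up schedules, depending on which section the site applies.

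**2. What data would be lost.** SAP Appendix A schedules HD-CAB, vital signs, ECG, laboratory tests and C-SSRS in the Day 42 or ET column. SAP Section 8.3.2 maps an ET measurement to a scheduled visit when none is available; the Day 14 window for HD-CAB is study days 2 to 20. An exit before Day 14 with an ET cognitive assessment therefore still supplies a post-baseline value, and the participant stays in FAS1 and FAS2. Loss from those sets needs both conditions: exit before any post-baseline test, and no ET cognitive assessment. Section 8.4.2 asks for the ET visit only if possible. In every case the scheduled visits after ET are lost.

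**3. The plan's own figures.** Inputs are from Protocol Section 13.8 and SAP Section 5.2.

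- Randomised: 32 / (1 − 0.20) = 40, as stated. The allowance is 40 − 32 = 8 participants.
- 80% half-width for one mean: z(0.90) × 1.51 / √n. At n = 16 this is 0.484 (0.506 with t), so the stated 0.50 reproduces per arm. At n = 15 it is 0.500, and at n = 14 it is 0.517.
- Two removals per arm make 4 in total, or 4 / 8 = half of the allowance.

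**4. Illustration of a selection effect.** None of these inputs is in the documents. Assume that k of 20 participants in one arm are removed, that they contribute no usable post-baseline value, and that their outcomes would have differed from the rest of the arm by g = 0.5 to 1.0 SD.

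- Shift in that arm's mean = (k / 20) × g.
- Ratio of standard errors for that arm's mean = √(20 / (20 − k)).

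| k removed | Shift, g = 0.5 SD | Shift, g = 1.0 SD | SE increase |
|---|---|---|---|
| 1 | 0.025 SD | 0.05 SD | 2.6% |
| 2 | 0.05 SD | 0.10 SD | 5.4% |
| 3 | 0.075 SD | 0.15 SD | 8.5% |

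For scale, the standard error of a 20-versus-20 difference is √(2 / 20) = 0.32 SD. The largest shift shown is 0.15 / 0.32 = 0.47 of that.

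**The case against.** The case against is substantial, and most of it limits the harm.

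- **A reader might infer that Section 7.1 lets only loss of consent or capacity end visits.** It does not go that far. It says participants should complete visits, it concerns those who stop IP, and it goes on to recognise that someone may stop study participation. The tension with 8.4 stands, because 7.1 names no compliance ground and 8.4 does.
- **A reader might infer that poor adherers must be removed, or that their data are deleted.** Neither is written. Section 8.4 is permissive, the 8.4.2 list gives possible reasons, and 10.5.1.1 asks for follow-up and discussion. Nothing discards data already collected.
- **Safety follow-up does not simply cease.** The ET visit carries the main safety assessments. Section 12.2.1 follows participants who stop IP because of an AE, 12.2.2 follows ongoing SAEs, and the Safety Set keeps every dosed participant with HD. An exit coded as non-compliance does not trigger the 12.2.1 rule for AE discontinuers, so scheduled observation after ET remains exposed.
- **The evaluable count has a backstop.** Section 8.4.4 allows additional randomisation if dropout exceeds 20%. That restores numbers; it does not recover the missing visits of those who left.
- **Blinding makes one-arm removal less likely.** It does not exclude it, since tolerability can drive adherence.
- **The treatment-comparison text in the SAP is largely redacted.** Any estimand or missing-data rule there cannot be judged.

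**Conclusion.** The inconsistency is in the current text and is worth correcting, because the correction is cheap and preserves visits already in the schedule. It does not threaten the primary result: baseline HD-CAB in HD versus healthy participants is measured before any such exit can matter. Exposure is confined to post-baseline SAGE-718 versus placebo data and to scheduled safety observation after the ET visit. Exclusion from FAS1 or FAS2 occurs only in the narrow case described in step 2.

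No bias has been demonstrated, and its size cannot be derived from the documents. The range of 0.025 to 0.15 SD rests on assumed counts, an assumed difference, removal from one arm only, and no usable data from those removed. It should not be quoted as an expected effect.

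**What to change.** - For participants with HD, state in Sections 8.4 and 8.4.2 that non-compliance with study drug or a protocol deviation is not by itself a reason to end study assessments. Compliance in 8.4 then applies to IP, and the Section 7.1 visit schedule continues.
- When IP is stopped in such a case, record the reason under IP discontinuation.
- Reconcile 8.4.1 with 7.1, 7.1.3 and SAP 5.1 in the same edit.
- Leave unchanged the decisions on when to stop IP, and exits for safety or by the participant's own choice.
- Keep a separate disposition category for healthy participants. They receive no IP, and the 8.4.2 list is not limited to HD.

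Deleting two labels from the 8.4.2 list would not be enough. The list is open and keeps physician decision and other, so the same exits could continue under less informative codes. The explicit statement is what makes the change work.

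The cost is wording in the named protocol sections and the eCRF disposition list. The downside is that sites carry out a few already scheduled visits in participants who are off drug or off protocol.

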8.4.1. Investigational Product Discontinuation

Participants who discontinue IP will be invited by the investigator to complete all of the scheduled study visits and assessments through the end of the Treatment Period. Those who decline to continue participation will be asked to complete an ET Visit.

8.4.2. Early Termination from the Study

At the time of study withdrawal/stopping study participation, if possible, an ET visit should be conducted. The participant will be permanently discontinued both from the IP and from the study at that time.

If the participant withdraws consent for disclosure of future information, the sponsor will retain and continue to use any data collected before such a withdrawal of consent.

If a participant withdraws from the study, he/she may request destruction of any samples taken and not tested, and the investigator must document this in the site study records.

Possible reasons for study discontinuation include but are not limited to the following:

- AE
- Pregnancy
- Protocol deviation
- Non-compliance with study drug
- Lost to follow-up
- Withdrawal by subject
- Screen failure
- Study terminated by sponsor
- Physician decision
- Other

8.4.3. Loss to Follow-up

A participant will be deemed lost to follow-up after 3 attempts at contacting the participant have been made and it has been at least 1 month since the last participant contact. All attempts of contact and the reason for discontinuation will be documented. If the investigator becomes aware of a change in the participant's status or receives more information about a participant's disposition, this information will be documented.

8.4.4. Replacement of Participants

Participants who discontinue or withdraw from the study will not be replaced. However, additional participants with HD may be randomized if the dropout rate is higher than 20%.

9. TREATMENT OF PARTICIPANTS

9.1. Description of Investigational Product

SAGE-718 oral softgel lipid capsules are opaque, white to off-white, oval capsules containing either 0.3, 0.6, 0.9, or 1.2 mg of SAGE-718 drug substance.

9.2. Prior Medications, Concomitant Medications, Restrictions, and Contraception Requirements

9.2.1. Prior and Concomitant Medications and/or Supplements

All medications and supplements taken within 8 weeks prior to Screening, all medications used to treat HD regardless of timing, and all nonpharmacological methods (eg, psychosocial, psychotherapeutic) used to treat or prevent neuropsychiatric, functional, and cognitive manifestations of HD will be recorded. Information regarding diagnosis and/or hospitalization due to coronavirus disease 2019 (COVID-19) will be documented as part of medical history, AE collection, and prior/concomitant medication/procedure collection at Screening and throughout the study.

At visits subsequent to Screening, all changes to any medication should be captured. All medications and/or supplements taken from the first dose of IP through the final study visit (including start and end dates, route, dose/units, frequency, and indication) will be recorded on the source document. Any concomitant medication determined necessary for the welfare of the participant with HD may be given at the discretion of the investigator at any time during the study.

Because this study aims to measure effects on cognitive performance, it is important to evaluate single or combined concomitant medications and their doses for their potential effects on cognition. Investigators will carefully review concomitant medications for possible cognitive effects at Screening to determine participant eligibility and throughout the study.

9.2.2. Prohibited Medications

Prohibited medications prior to and during the study include:

- Gene therapy
- HD investigational drug, biologic, or device within 180 days prior to Screening and until the final visit
- Non-HD investigational drug, biologic, or device within 30 days or 5 half-lives (whichever is longer) prior to Screening and until the final visit

Use of the following medications is prohibited within 30 days of screening and during the entire course of the study:

- Medications that inhibit cholesterol absorption (eg, ezetimibe).
- Bile acid sequestrants (eg, colestevam, colestipol, cholestyramine).

- Medications with potent effects at the NMDA receptor, including memantine, amantadine, cycloserine, ketamine, or related compounds.
- THC-containing substances (any route of administration), regardless of whether or not they are prescribed

Any medication determined necessary for the welfare of the participant may be given at the discretion of the investigator at any time during the study; however, the use of any prohibited medications will be captured as a protocol deviation.

9.2.3. Other Restrictions and Recommendations

Participants must agree to refrain from drugs of abuse for the duration of the study (unless deemed by the investigator to reflect a prescribed medication) and from alcohol during the 48 hours preceding each study visit.

Psychotropic medications and medications that are known to affect cognitive performance (ie, antidepressants, anxiolytics, stimulants, benzodiazepines, antipsychotics, anticholinergics) must be at a stable dose for at least 30 days prior to the first IP administration. Additions and/or modifications to these medications should be minimized throughout the course of the study.

Other medications given at doses, frequencies, or in combinations that are likely, in the opinion of the investigator, to have a deleterious effect on cognitive performance are to be avoided as much as possible.

Any additions or modifications to medications during the course of the study will be recorded in the concomitant medications log and source documentation.

9.2.4. Acceptable Forms of Contraception

As per the Clinical Trials Facilitation and Coordination Group (CTFG), a female is considered of childbearing potential (FOCBP) ie, fertile, following menarche and until becoming postmenopausal unless permanently sterile. Permanent sterilization methods include hysterectomy, bilateral salpingectomy and bilateral oophorectomy.

A postmenopausal state is defined as no menses for 12 months without an alternative medical cause and confirmed by follicle-stimulating hormone [FSH] > 40 mIU/mL). A high follicle stimulating hormone (FSH) level in the postmenopausal range may be used to confirm a postmenopausal state in females not using hormonal contraception or hormonal replacement therapy. However, in the absence of 12 months of amenorrhea, a single FSH measurement is insufficient.

A male is considered fertile after puberty unless permanently sterile by bilateral orchidectomy.

Acceptable forms of highly effective contraception (ie, can achieve a failure rate of <1% per year when used consistently and correctly) for participants of childbearing potential or for a male participant's partner of childbearing potential include:

- Sexual abstinence;
- Combined (estrogen and progestogen containing) oral, intravaginal, or transdermal hormonal contraception associated with inhibition of ovulation;

- Oral, injectable, or implantable progestogen-only hormonal contraception associated with inhibition of ovulation;
- Intrauterine device;
- Intrauterine hormone-releasing system;
- Bilateral tubal ligation or bilateral tubal occlusion (performed at least 3 months prior to Screening);
- Vasectomized partner (performed at least 3 months prior to Screening). (Note: vasectomized partner is a highly effective birth control method provided that partner is the sole sexual partner of the participants of childbearing potential and that the vasectomized partner has received medical assessment of the surgical success.)

Acceptable forms of contraception for male participants include:

- Sexual abstinence;
- History of vasectomy (performed at least 3 months prior to Screening);
- Condom with spermicide used together with highly effective female contraceptive methods if the female partner(s) is of childbearing potential (see above for list of acceptable female contraceptive methods).

